Orthopaedic Surgery Research

[contact] • 4A144B

Email address: [contact]

PROTOCOL 3.5 2/8/2017

Study Title: Comparative Effectiveness of an Activity-Specific Monitoring Device (StepRite) on Short Term Outcomes in Adults after Total Knee Arthroplasty

Principal Investigator	Department	School/Campus	Email Address
[name]	Orthopaedic Surgery	SOM Lubbock	[contact]
Sub Investigator's			
[name]	Orthopaedic Surgery	SOM Lubbock	[contact]
[name]	Orthopaedic Surgery	SOM Lubbock	[contact]
[name]	Orthopaedic Surgery	SOM Lubbock	[contact]
[name] PT DTP	UMC Physical Therapy	Lubbock	[contact]
[name]	Orthopaedic Surgery	SOM Lubbock	[contact]
[name], CCRC	Orthopaedic Surgery	SOM Lubbock	[contact]

Abstract:

Partial Knee Arthroplasty (PKA) or Total Knee Arthroplasty (TKA) is a procedure commonly used in severe degeneration of the knee joint due to osteoarthritis. With an increasing number of PKA's and TKA's performed in a population that is aging during a time where the amount of healthcare dollars allotted to rehabilitation is declining, there is a need to develop remote monitoring of rehabilitation and to engage and optimize self-management of recovery.

Current management of PKA and TKA recovery is typically performed in the out-patient setting and is highly protocol driven. A typical case might be seen by the physical therapist 2-3x/week for 8-10 weeks to perform specific exercises and to monitor progress (i.e. compliance with ROM and strengthening exercises). One recent study suggested that variation in patients' independent exercise and activity after arthroplasty surgery may contribute to variable functional gains [1].

We are proposing that the StepRite device developed by MedHab, (a shoe insert that collects functional data) will reduce cost and improve the efficacy of rehabilitation in total knee arthroplasty patients.

Background

Tele-rehabilitation is an emerging method of delivering healthcare. It is likely to become more prevalent as technology improves and funding for clinic appointments diminishes. Recent studies have shown that tele-rehabilitation can be as effective as conventional treatment, as is well tolerated by both patients and healthcare professionals [2, 3].

The StepRite system developed by MedHab (<http://www.medhab.com/>) allows the physical therapist to monitor physical activity and exercise remotely, thereby reducing the need for frequent out-patient visits. A thin insole placed inside the shoe measures foot contact pressure and acceleration. This information is translated into quantitative feedback about exercise compliance and performance measures comparing the surgical side with the non-surgical side. Real time feedback during exercise and weight-bearing activities is

provided to the patient, and a HIPAA secured user interface website also displays this information in an online dashboard for both physical therapists and the physician.

With the advent of federally mandated bundled payments for total joint replacement, active management of the rehabilitative process postoperatively with quantifiable data will be necessary to ensure financial stability.

Given the potential for improving patient engagement with rehabilitation, this study proposes a treatment model which includes monitoring activity outside of the clinic using the StepRite device and using a combination of outpatient appointments and remote consultations with therapists.

Significance of this study

The significance of the proposed study includes the projected benefit to the patients in terms of attaining clinical outcomes quicker and to the medical system in terms of managing cost for the provision of services. Subjects are expected to demonstrate improved compliance to patient tailored rehabilitation protocols which will lead to more rapid attainment of clinical outcomes versus present traditional rehabilitation methodologies. The expected level of, and rate of, attainment of clinical outcomes will translate to an overall reduction of cost to the medical system by reducing the need to engage in additional processes or the need to protract the time required to attain clinical outcomes, where either or both in combination can increase rehabilitation expenditures.

Objectives

To compare the efficacy of StepRite in a prescribed physical therapy program verses traditional in-facility physical therapy program after partial or primary total knee replacement using validated survey tools to evaluate patient progress, including patient self-reporting of progress and surgeon appraisal of patient performance post-operatively.

To compare the overall cost of post-operative rehabilitation of patients involved in traditionally employed regimens versus those using the StepRite device.

Hypothesis and specific aims

The aim of this study is to evaluate whether improved clinical outcomes as well as reduction in cost in provision of care can be better affected through the use of the Steprite device as compared to the use of traditional rehabilitation modalities.

We will seek to reject the null hypotheses that 1) there is no difference between clinical outcomes attained between patients using the Steprite device and those using traditional rehabilitation modalities and that 2) there is no reduction in cost to the medical system when patients use Steprite versus other conventional methods of rehabilitation.

By rejecting the null hypothesis we will accept the alternate hypothesis that, through the use of the Steprite device, not only will patients achieve overall clinical outcomes faster but there will be an associated decrease in cost burden to the medical system and the differences observed will be statistically significant as compared to rehabilitation of patients not using the Steprite device.

Patients who use the device post-surgery will demonstrate superior short-term improvements (i.e. 3 months post-surgery) with respect to self-reported functional outcomes and gait parameters, compared to a control group not using the device. The patients will self-report through the use of validated survey instruments including the KOOS survey (knee injury and osteoarthritis outcome score), LEFS (lower extremity functional scale) and/or KSS (knee society score), the latter of which includes a section for surgeon evaluation of patient functionality post operatively.

Study Design and Methods

This is a point of care clinical trial; a trial that functions to integrate research within a clinical setting that has the ability to readily deliver either modality of the proposal. This type of study design relies on provider referral of patients to be approached for consent, after which randomization to one of two treatment groups is facilitated; a control group of 15 patients participating in conventional rehabilitation regimens and an experimental group of 15 patients who will participate in the same rehabilitation regimen but facilitated

through the use of Steprite. Importantly, care for patients is delivered as part of current adopted standards utilizing outcome measurements, the use of which and the interpretation of which is already built into care provided by the clinical facility, thereby negating the need to develop additional outcome measures. Recruitment of 30 patients will come from the investigators' normal patient population, among patients who are scheduled for partial or total knee arthroplasty. As there is no change in post op care for these patients from the investigators standard protocols other than monitoring and enforcement of home protocols, the same therapists involved in investigators' normal patient care will be involved with both arms of the study.

For this study, 30 patients represents a sample size deemed acceptable as a starting point. There are no other published studies using Steprite in comparative design trials. Determinations of sample size needed for this study, using 80% power and significance of 0.05, incorporate the use of a time frame in days or weeks for completion of the rehabilitation protocols that would allow for the detection of clinically significant differences between the group using Steprite and those using conventional therapies only. Given that conventional therapies can include skilled nursing, home health and outpatient visits and given that the need for each of these is highly variable dependent on the patient, it is difficult to assign a time value for determinations of sample size.

With that, a sample size of 30 participants divided into two groups represents an initial starting point, with the potential of incremental addition of more patients in order to achieve significance between the two study groups.

Statistical significance will be evaluated utilizing a standard t-test for two group comparison.

In preparation for the study, MedHab Inc. will at their expense train all involved investigators and therapists in the fitting and use of the StepRite device. Medhab will also train a lead therapist designated by the lead investigator to be in charge of overseeing and monitoring, ensuring proper use of the device. There is no cost to the patient, hospital or other funding entity for participation in this study. Medhab LLC will assume all costs associated with the training, application, device and use of the StepRite product for the full course of this study.

Subjects for this study will be recruited from the patient population seen by the investigators during the normal course of business. There will be no outside recruitment of individuals or advertising as to the presence or use of the monitoring device to entice new patient referral. Prospective candidates will be asked by the lead investigator at the time they are designated surgical candidates. All documentation related to the study will be reviewed with the patient by the lead physician or his designee who is appropriately trained in discussing patient recruitment. Final decision and randomization to control or StepRite use will be done as part of the preoperative checkup just prior to surgery where both operative consent and study consent are discussed and signed.

Randomization:

Once a patient agrees to the study they would be sequentially randomized into whether or not they receive StepRite. The patients will be randomized to every other eligible patient gets the intervention. (ie: 1,3,5,7,9... will get StepRite ; 2,4,6,8 will not get StepRite) 15 Intervention subjects will be recruited and 15 control subjects will be recruited with an extra 5 patients to account for attrition and withdrawals.

Schedule of events

The intervention group will receive the StepRite device with standard conventional care and the control group will receive standard conventional care only. Both groups will receive outpatient, home health, and /or 24 hour physical therapy treatment plans per their surgeon's standard of care. The control group will undergo the conventional outpatient treatment program to 8 weeks as normally prescribed by the lead investigator. This consists of a twice weekly outpatient appointment with a physical therapist and prescribed home exercise program (see attached physical therapy protocol).

The patients randomly selected to wear the StepRite inserts will be fitted and instructed along with the patient's designated care giver in their use including initial pre-op measurements prior to their surgical date so that data collection can begin on the 1st day of rehab after surgery

Those patients not selected to wear step rite will receive instructions preoperatively of their expected therapy regimen and receive their baseline functional evaluation of the knee

Both groups will be given log sheets to record their activity at home and when seen by the physical therapist. These will be returned and collected by the therapist weekly and scanned into/ kept in the patient's medical record file. A paper copy will be kept in the coordinator's office, 4A144B with the consent forms and any other study documents.

Both groups will also have routine self-assessment questionnaires (appendices 3, 4 KOOS and KSS) and functional testing performed by the PI and PT during the patient's regular clinic visit as standard of care.

Outcome measurements performed just after surgery and at time of discharge from hospital and standard of care post-surgical clinic visits to 8 weeks will indicate if any patients are experiencing unexpected delays in progress. Subjects will be visited at home by the Home Health therapists, and will visit and receive telephone consultations with the outpatient therapists, who will be able to monitor the patients' conditions and intervene if there are any problems related to the use of the device. The StepRite device will provide the therapist with more information about the patients' activity levels and progress than would usually be available to them and so is not expected to have any safety implications. The device and App. will prompt the patient with voice and text to complete their exercises as they are needed, while collecting data.

Device Flow Chart: standard of care post-op

The research coordinator will consent the patient prior to the surgery

The research coordinator will document the following information for the device on the device data collection form. (See attached)

- a. Name of patient
- b. Email of patient
- c. Phone number of patient
- d. Surgery date
- e. Expected date of discharge

The patient's information will then be entered into the steprite™ system and a patient account will be created by the Research Coordinator

Physical therapy will schedule the study protocol via the steprite™ system and enter the physical therapy start date as day after discharge.

MedHab™ sponsor ([name]) will contact the patient for the patient account set up and to obtain the following signatures required by MedHab (see attached)

- a. HIPAA
- b. Assignment of Benefits

MedHab™ will help the patient load the app, provide an overview of the app, and forward a tutorial video
MedHab™ will send the steprite™ device to the study Research Coordinator at TTUHSC

TTUHSC Orthopaedic Surgery

Clinical Trials Coordinator, [name]

[name]

(t)[contact] (f)[contact]

The Research coordinator will fit the patient with the device, pair, and connect the device at time of discharge.

Patient will leave the hospital with the steprite™ device and instructions to charge device overnight for use the next day.

Patient will begin exercise regimen prompted by the StepRite App on the cell phone.

Physical therapy will communicate with the patient per the therapy protocol

Physical therapy is to work with patient per standard of care protocol with the addition of 3 patient outcome surveys, (KOOS, KSS, and the Lower Extremity functional scale) (see attached) at 4, 6, and 8 weeks post op, and the PI will see the patient as standard of care at visits 2, 6, and 12 weeks post-op. The 2 week patient outcome surveys will be completed at the 2 week standard clinic visit with the assistance of the study coordinator. All documents and data collection forms from physical therapy and clinic will be

scanned into the patients chart for review and kept in a locked file cabinet in the research coordinators office 4A144B.

Physical therapy advises the PI and MedHab two weeks prior to close of therapy on close out or extension procedure if needed.

The PI and MedHab extends the therapy or communicates the close out procedure with the patient.

Control Subject flow

The control group will have all Post-op standard of care as the device group without the use of the device.

Device Information

The device to be used in the study is the StepRite, manufactured and supplied by Medhab LLC. The device is considered exempt from IDE regulations, as it is a diagnostic device. It has been approved as a Class I medical device by the FDA.

The StepRite device consists of a thin insole which is placed inside the shoe.

The insole contains pressure sensors which record pressure data when exercises are performed, and contains an accelerometer, which records acceleration of the foot and is used to calculate velocity and activity levels.

A wireless connection between the insole and a cell phone application allows transfer of data.

The cell phone application will be supplied.

The cell phone application displays real-time feedback of pressure distributions to the user, and connects wirelessly to the Medhab servers to upload data onto the secure web interface, for access by the physical therapist or physician.

The device does not impart energy to the user.

The patient or designated care giver will be responsible for placing the insoles on their charging platform nightly.

Indicate the number of patients/charts/surveys/specimens needed.

The total number of patients needed in this study is 30, we will request a total of 35 to account for possible Attrition or withdrawals. 15 will be fitted with the StepRite device and 15 will follow the normal postoperative protocol without the device and be considered control subjects.

Inclusion criteria

Unilateral Partial or Total knee arthroplasty.

Age 45-75 yr. old

BMI <35

Access to Wi-Fi

Have appropriate smart phone and knowledge of use

Be willing to place StepRite app on their personal phone

Exclusion criteria

History of neuromuscular disorder (e.g. Parkinson's, Polio, or stroke).

Pregnancy

History of cognitive disease that would preclude ability to navigate smart phone

Method of identifying and recruiting subjects.

Recruitment will come from the investigators normal patient population who are scheduled for a partial or total knee replacement. The Investigators will identify and consult the research coordinator to assess eligibility.

Compensation given to subjects.

There will be no compensation given to subjects. They will be allowed to keep the insoles and access the app for at home therapy at no cost to them for as long as the device works.

Describe the site(s) where study will be done.

The main clinical/surgical portion of the study will take place at Texas Tech University Health Sciences Center department of Orthopaedic Surgery and University Medical Center Lubbock. The physical therapy departments used for this study will be the investigators preferences and standard of care, therefore they would be used if not on the study and are not study specific.

MedHab LLC (StepRite) will be collecting data from several sites to compare outcomes and cost. The secondary sites utilizing this device and doing similar studies are Covenant with [name] as the lead investigator, the Lubbock Heart Hospital with [name] as the lead investigator, and Texas Health Resources with [name] as lead investigator. All the secondary sites will use their standard of care preferences for clinical/surgical and physical therapy. TTUHSC will not be collecting data nor in any way be affiliated with the secondary study sites. They will acquire their local IRB approval for each site separately using similar device protocols.

Risks

There is a risk of loss of confidentiality, we will have measures in place to help prevent any loss of personal information. During the course of this study there are no new or additional steps required of the subjects from what is considered the standard protocol for the lead investigator. The only alteration may be reduced travel and outpatient visit by the patient if compliance and functional improvement noted by the therapist. StepRite imparts no energy to the patient and poses no hazard to patient well being. Subjects will be free to withdraw from the study at any time and revert to conventional rehabilitation treatment.

Possible benefits to subjects

There is a possibility the device group patient could benefit from the device prompting them to do their own exercises regularly, which could lead to a faster recovery and better physical therapy outcomes. We are hoping the participation in this study may help us learn how we can design rehabilitation programs to be more effective in the future.

Confidentiality measures

StepRite / MedHab will have access to non-PHI patient data collected by the device stored on their HIPPA compliant server and be available only to the lead investigator. All PHI will be kept separate from the study data in a locked filing cabinet or on a password protected computer in the research coordinators office in 4A144B.

Data Collection and Monitoring

Data recorded by the StepRite device will be transmitted wirelessly to the HIPAA secured web interface managed by Medhab. Clinicians will be able to log into the website with a password to review the progress of each patient.

Data recorded by the PI and physical therapist on the functional motion of the knee will be recorded in paper form and kept with the completed KOOS questionnaire and Knee Society Score (KSS) and scanned into the patients HIPPA protected chart.

Upon completion of patient's part in the study MedHab will contact UMC and the Therapy departments to acquire actual costs of these services. This will be done to compare the overall cost of management of the post-operative rehabilitation of a patient in traditional rehabilitative regimen vs. use of StepRite,

Actual Cost information for the patient's full rehabilitation will be requested and collected by the Hospital and released to MedHab at the end of the study and supplied to the lead investigator for analysis.

References

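### Rejecting a null about the level of outcome is taken to show 'faster' recovery, but no speed outcome or analysis is defined

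*Combined protocol and SAP*

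**What the plan says.** - 'Significance of this study' expects "more rapid attainment of clinical outcomes versus present traditional rehabilitation methodologies".
- 'Hypothesis and specific aims' states the first null as "there is no difference between clinical outcomes attained between patients using the Steprite device and those using traditional rehabilitation modalities". On rejection, the alternative to be accepted is that "through the use of the Steprite device, not only will patients achieve overall clinical outcomes faster". The same section expects "superior short-term improvements (i.e. 3 months post-surgery) with respect to self-reported functional outcomes and gait parameters", reported through KOOS, LEFS and/or KSS.
- 'Study Design and Methods' gives one analysis, a standard two-group t-test, with no outcome, week or sidedness attached. It says that the sample-size determinations "incorporate the use of a time frame in days or weeks for completion of the rehabilitation protocols", and then that a time value is hard to assign because care needs differ so much between patients. It describes the device arm as "an experimental group of 15 patients who will participate in the same rehabilitation regimen but facilitated" by StepRite.
- 'Schedule of events' says: "The control group will undergo the conventional outpatient treatment program to 8 weeks as normally prescribed by the lead investigator". It adds: "This consists of a twice weekly outpatient appointment with a physical therapist and prescribed home exercise program". It also gives both groups KOOS, KSS and functional testing at regular clinic visits.
- 'Device Flow Chart' lists KOOS, KSS and LEFS at weeks 4, 6 and 8, with week-2 surveys done in clinic, and standard-of-care visits to the principal investigator at weeks 2, 6 and 12. It leaves close-out or extension of therapy to the principal investigator and the device supplier.

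**The concern.** The null and the conclusion drawn from rejecting it are about different quantities. A t-test on scores asks whether the arms differ in mean function at the week tested. It does not ask when a given level of function was reached. Speed is not stray wording here: the significance section rests the patient benefit, and the expected cost saving, on quicker attainment.

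If the plan is followed as written, a significant score difference at any week would be reported as faster recovery. In the other direction, a null result at 3 months could be read as no gain in speed, although the arms may have differed early and then converged. A reader looking for a direct measure of time would find only programme completion time, which does not measure recovery cleanly.

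**Working it through.** **Step 1. Match the conclusion to what is measured.**

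- Null: outcomes attained, which is a level. The only time attached to expected improvement is 3 months.
- Conclusion: outcomes reached sooner, which is a time or a rate.
- Analysis: a two-group t-test, with no milestone, early week, slope or time-to-event method.

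A higher device-arm mean at 3 months is compatible with arms that were equal, or even reversed, through week 8. Equal means at 3 months are compatible with quicker early recovery in one arm. Neither result settles the speed question. Rejecting 'no difference' also does not by itself give the direction.

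**Step 2. Ask whether the one time variable could fill the gap.**

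Time to complete rehabilitation is named for sample sizing only. 'Schedule of events' runs the control outpatient programme to 8 weeks by prescription. The device flow chart gives close-out or extension to the principal investigator and the supplier, who know that the patient has the device, and the visible text gives no functional criterion. Programme length therefore reflects prescription and discretion as well as recovery.

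**Step 3. Check which data could show speed.**

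KOOS and KSS are repeated in both groups at regular clinic visits. The week 2, 4, 6 and 8 timing appears in the device flow chart, where the week 4, 6 and 8 surveys are described as an addition to standard care. 'Control Subject flow' gives controls the same standard care without the device. Whether controls complete the added surveys, and LEFS at all, is therefore unclear. For baseline, the visible text mentions preoperative measurements (device arm) and a functional evaluation of the knee (controls), but no preoperative KOOS.

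**Step 4. What 15 per arm can detect.**

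The planned 30 cannot be reproduced, because no difference or SD is given. The inputs are 15 per arm, 80% power and alpha 0.05, all from the protocol; two-sided testing is my assumption.

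- Difference in means: (1.960 + 0.842) × √(2/15) = 1.02 SD by the normal approximation, or 1.06 SD with the exact t.
- Time to a milestone (Schoenfeld), assuming that all 30 patients reach it: ln(ratio) = (1.960 + 0.842)/√(30 × 0.25) = 2.802/2.739 = 1.023, so the ratio is exp(1.023) = 2.78.

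The documents give no rate ratio, so a range is assumed:

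| Assumed rate ratio | Events for 80% power | Power with 30 events |
|---|---|---|
| 1.5 | 191 | 20% |
| 2.0 | 66 | 47.5% |
| 2.5 | 38 | 71% |

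These figures treat attainment times as known exactly. Visits two or more weeks apart would not improve on them.

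**Step 5. Why the speed analysis must be single and prespecified.**

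If 'faster' could be read from any of 3 instruments at 4 visits, there would be 12 tests at 0.05. If independent, the chance of at least one false positive is 1 − 0.95^12 = 46%. These tests are correlated, so the true figure is lower.

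**The case against.** The strongest reply is that the protocol does not declare completion time as an outcome. Its efficacy objective rests on validated surveys and surgeon appraisal, repeated from early after surgery. If function rises steadily and the arms start level, a higher score at an early week means that the device arm reached the control arm's level sooner. On that view the data can show speed, and only the analysis is unstated. This stands as far as the data go. It does not rescue the stated inference, because no early week or trajectory is chosen and the only time given for improvement is 3 months.

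A reader might infer something stronger: that controls are locked into 8 weeks while device patients can be closed out early, so a shorter StepRite programme is built in even with identical recovery. The documents do not support that.

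- The 8 weeks refers to the outpatient programme, and 'Abstract' gives 8-10 weeks as typical.
- 'Study Design and Methods' says that the need for each component of care varies widely, and puts the device arm on the same regimen.
- 'Risks' allows fewer visits when improvement is noted, not an earlier end of therapy.
- The device flow chart also allows extension.
- The attached physical therapy protocol is not visible and may contain discharge criteria.

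**Conclusion.** The point holds as one of inference and endpoint definition. The protocol moves from a null about level to a conclusion about speed, and nothing in the visible text defines how speed would be measured or analysed in either arm. Completion time would not be sound evidence of recovery speed if it were used, but no passage says that it will be, and no size can be put on any bias from it.

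Nor does it follow that the trial can say nothing about speed: repeated KOOS in both arms could be used. What limits that route is precision. A milestone analysis reaches 80% power only at a rate ratio of about 2.8, assuming two-sided 0.05 and that all 30 patients reach the milestone. The verdict rests on the visible text; the attachments could add therapy discharge criteria or survey details.

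**What to change.** 1. In 'Hypothesis and specific aims', limit 'faster' to one prespecified speed analysis on an instrument that both arms complete at the same visits. Two options:
   - a between-arm comparison of the early KOOS function trajectory (change from baseline across the repeated early assessments);
   - the first scheduled assessment at which a prespecified KOOS level is reached, analysed as interval-censored.
2. State that the week 2, 4, 6 and 8 surveys apply to controls, or use only visits common to both arms. Confirm that a baseline KOOS is taken in both arms if change from baseline is used.
3. If no speed analysis is added, restate the conclusion as a difference in function at a named week.
4. State that programme completion time will not be used as evidence of recovery speed. Reconcile 'Study Design and Methods', 'Schedule of events', 'Device Flow Chart' and 'Risks' on programme length, visit reduction and close-out.

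The cost is protocol wording and a modest analysis of surveys that are largely scheduled already, plus any control-arm or baseline surveys not now collected. The downside is that visit spacing makes attainment time coarse and, given the power above, the milestone analysis should be labelled supportive.

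### The 3-month superiority prediction has no survey assigned to week 12 and no gait measure named for both arms

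*Combined protocol and SAP*

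**What the plan says.** Hypothesis and specific aims predicts that patients using the device will show "superior short-term improvements (i.e. 3 months post-surgery) with respect to self-reported functional outcomes and gait parameters, compared to a control group" not using it. It lists KOOS, LEFS and/or KSS as the self-report instruments. The same section says that "patients achieve overall clinical outcomes faster" with the device.

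Three places bear on when the questionnaires are given:

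- The Device Flow Chart adds KOOS, KSS and LEFS to physical therapy at weeks 4, 6 and 8, and has the week-2 surveys completed at the week-2 clinic visit. It puts the principal investigator's visits at weeks 2, 6 and 12.
- Schedule of events gives both groups "routine self-assessment questionnaires (appendices 3, 4 KOOS and KSS) and functional testing performed by the PI and PT" at the "regular clinic visit as standard of care", without naming a week. It also says that outcome measurements just after surgery, at discharge, "and standard of care post-surgical clinic visits to 8 weeks will indicate if any patients are experiencing unexpected delays in progress".
- Study Design and Methods describes the use and interpretation of the outcome measurements as "already built into care provided by the clinical facility".

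On gait, Device Information describes an insole that records pressure and acceleration and yields velocity and activity levels. Under Control Subject flow, controls have the same standard post-operative care without the device. Before surgery, controls "receive their baseline functional evaluation of the knee". Data Collection and Monitoring refers to investigator and therapist records of knee motion. For therapy content, Schedule of events says "see attached physical therapy protocol"; that attachment is not part of the text available here.

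**The concern.** A between-group prediction with a stated time point needs the same measure, taken at that time, in both arms. The planned analysis, a two-group t-test, needs this too. On timing, the survey dates stop well before 3 months. On gait, the outcome is promised but never defined, and the one instrument described that could supply movement data is worn in one arm only.

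A site that follows the text could finish follow-up without week-12 questionnaires. The self-report prediction could then be examined only at week 8. Insole data alone would describe the device arm and could not support a comparison. Week-12 responses that were never collected cannot be recovered later.

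**Working it through.** The plan states no figure to reproduce. The check sets the sections side by side, with simple date arithmetic.

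**1. Gap to the predicted time point.** Dated surveys (Device Flow Chart) are at weeks 2, 4, 6 and 8. The last is 8 × 7 = day 56. Twelve weeks is 12 × 7 = day 84; three calendar months is about 13 × 7 = day 91. The gap is 84 − 56 = 28 days to 91 − 56 = 35 days, or 4 to 5 weeks.

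**2. Investigator visits against survey weeks.** Visits are at weeks 2, 6 and 12. Weeks 2 and 6 are dated survey weeks; week 12 is not. So 2 of 3 visits coincide with a survey, and the one that does not is the one the prediction needs. The flow chart attaches surveys to the week-2 clinic visit in words and has no matching statement for week 12.

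**3. Instruments at week 12, on each reading.**

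| Reading | KOOS | KSS | LEFS | Count |
|---|---|---|---|---|
| Named in the text | no | no | no | 0 of 3 |
| Undated clinic questionnaires taken to cover week 12 | yes | yes | no | 2 of 3 |

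LEFS is absent either way. Because the hypothesis joins the instruments with and/or, losing LEFS narrows the comparison but does not remove it.

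**4. Whether the dates apply to both arms.** The dated surveys sit in the device flow chart, as an addition to standard care. Controls are given the standard care that the device group has. Schedule of events does give KOOS and KSS to both groups, but without weeks. The text therefore does not state that controls follow the dated schedule, or that they complete LEFS.

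**5. Gait.** In the body of the protocol the word appears once, in the prediction itself. Parameters defined: 0 in either arm. Described instruments that record foot motion: 1 in the device arm (the insole), 0 in controls. The clinician-recorded items that are named concern the knee. The functional testing by investigator and therapist is not defined. Reference 7 is a validity study of a photoelectric gait system, but the body cites only references 1, 2 and 3 of the 8 listed.

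**6. Baseline.** The prediction is of improvements. Schedule of events mentions pre-operative measurements for the device arm and a knee evaluation for controls, but names no pre-operative KOOS, KSS or LEFS in either arm.

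**The case against.** The strongest reply reads Schedule of events and the Device Flow Chart together. Both groups have KOOS and KSS at routine clinic visits, and the investigator's routine visits include week 12, so the ordinary reading is that both are collected then in both arms. The KSS has a surgeon-evaluated section, which points to completion at surgeon visits, and Data Collection and Monitoring keeps KOOS and KSS with the clinicians' functional data. The mention of 8 weeks comes in a sentence about spotting slow progress and does not set an end to outcome collection. The attached therapy protocol and forms might define a gait test. Finally, the Objectives mention neither gait nor 3 months, and 3 months only glosses what is meant by short-term.

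Much of this is fair. KOOS and KSS may well be collected at week 12, the 8-week phrase is weak evidence against it, and an attachment could contain a gait measure. It remains true that no section assigns a questionnaire to week 12, that LEFS is missing on the favourable reading too, and that no gait measure common to both arms is named. An inference that depends on local habit is not an assurance that both arms will be measured alike at the predicted time.

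**Conclusion.** The concern holds and should be fixed. The plan's only dated, directional outcome prediction is not matched by its schedule or its named measures. The last dated survey precedes the predicted time point by 4 to 5 weeks. Between 0 and 2 of the 3 instruments are available at week 12, depending on the reading. From the measures named in the text, the between-group gait comparison cannot be made.

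The limits are clear. A week-12 visit exists, so this is not an absence of 3-month follow-up. The formal null hypotheses name neither a time point nor gait and remain testable. Confidence is medium, because the conclusion rests on the protocol text without its attachments, which could define a gait test or a week-12 form.

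**What to change.** Put the questionnaires in one dated schedule that is stated to apply to both arms, and reconcile the hypothesis, Schedule of events and Device Flow Chart with it.

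- **Self-report.** Either list KOOS, KSS and LEFS at the existing week-12 visit and name week 12 as the time point for the 3-month prediction, keeping weeks 2 to 8 for the hypothesis about speed of recovery; or restate the prediction at 8 weeks.
- **Baseline.** State in the same schedule whether a pre-operative score is taken in both arms.
- **Gait.** If the functional testing or the attached therapy protocol already includes a gait measure taken the same way in both arms, name it, its parameter and its visits. Otherwise remove gait from the between-group prediction and report insole data as descriptive results for the device arm only.

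The cost is one table, revised hypothesis wording, and a few minutes of questionnaire and coordinator time at a visit patients already attend (LEFS only, if KOOS and KSS are already routine there). The drawback is a narrower claim if the 8-week option is chosen or no common gait measure exists.
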